3.0 Participant Eligibility Criteria. This study will involve n=345 Veterans with symptomatic knee OA. All participants must meet the following criteria: 1) Diagnosis of Knee OA (identified from VA electronic medical records and self-report) and 2) Current Joint Symptoms (based on self-report). In particular, participants must self-report having an average knee pain of 3 or greater (on a scale of 0-10) over that past two weeks. Patients meeting the following criteria will be excluded: Currently completing PT visits for knee OA; Gout (in knee),

rheumatoid arthritis, fibromyalgia, or other systemic rheumatic disease; Dementia; Psychosis; Active substance abuse disorder; meniscus or ACL tear in the past 6 months; total joint replacement, other major lower extremity surgery in the past 6 months or planned in the next 9 months (e.g., wait list or referred to non-VA care for Orthopedic surgery); Severe hearing or visual impairment; Serious / terminal illness; Other health problem that would prohibit participation in the study and/or warrant immediate PT; Current participation in another OA intervention study; Unstable angina; History of ventricular tachycardia; Unstable chronic obstructive pulmonary disease (two hospitalizations within the previous 12 months and/or on oxygen); Uncontrolled hypertension (diastolic blood pressure >110 mm/Hg or systolic > 200mm/Hg, measured at the baseline visit); Stroke with moderate to severe aphasia, recent history of three or more falls (follow-up questions by a clinician will determine whether patient is likely at risk for continued falls and would therefore not be a good candidate for a new home exercise program), resident of a long-term care facility, hospitalization for a cardiovascular condition in the past 3 months.

Based on patient populations at our planned VA sites and experience from our previous studies, there will be an ample number of patients eligible for the proposed study. In a recent data pull, there were 3,039 patients at the Durham VAMC and 882 patients at the Greenville VAMC who had ICD-9 codes indicating knee OA and no codes for our exclusion criteria. In our completed trial, *Self-Management of OA in Veterans: A Telephone-Based Intervention*, 29% of patients who met initial eligibility criteria based on ICD-9 codes were ultimately eligible and consented to participate. Based on our recent data pull, this would result in approximately 1,137 enrolled participants for the proposed study.

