4.0 Enrollment Procedures.

We will recruit participants in three ways, which we have successfully employed in prior VA clinical trials: 1.) *self-referral*, 2.) *provider referral*, 3.) *direct contact* by the study team. *Self-referral* will involve placing posters and brochures in clinic waiting rooms and other common areas, as well as on the closed circuit television. VA clinicians may also give these brochures to patients who may be interested in the study. To facilitate *provider referral*, we will meet with primary care providers to inform them about the study and give study information by email and paper forms. We will set up a consult for referring patients to the study within the electronic medical record. Methods for *direct contact* of patients by the study team will begin with a data pull of patients who have ICD codes for knee OA and no exclusionary diagnoses, followed by an introductory letter. For participants recruited via all three methods, the study team may review VA medical records to verify a diagnosis of knee OA and lack of exclusionary diagnoses. The study team will also administer a screening questionnaire via telephone to further assess eligibility. If patients meet screening criteria and are interested in participating, they will be asked to come to their VA clinic for a baseline visit, which will consist of consent and baseline assessments. Study exclusion criteria (described above) that may make it unsafe to participate in regular activity will be assessed at multiple time points during the enrollment process. First, they will be identified from electronic medical records at the initial data pull (prior to sending out recruitment letters). Second, they will be included in the telephone-based screening questionnaire described above. Third, research assistants will scan participants' medical records prior to the baseline assessment to ensure these have health problems have not emerged since the phone screening. Fourth, at the baseline visit research assistants will ask participants if they have had any health changes or new symptoms since the phone screener. At the baseline visit, trained research assistants will measure participants Resting Blood Pressure using a digital sphygmomanometer after the consent process. Participants with diastolic blood pressure >110mm/Hg or systolic >200mm/Hg will be advised to be seen at the Emergency Department or Urgent Care immediately. Participant will not be able to continue until given a clearance. Elevated BP may be detected by trained research assistant at the baseline visit. Participants with signs of acute end-organ damage such as current chest pain, dyspnea (difficult or labored breathing) at rest, new onset of blurry vision, or new neurological deficits consistent with a stroke will be advised and assisted in seeking emergency medical care. We note that our total sample size goal of n=345 pertains to the number of participants who complete baseline assessments and are informed of their randomization assignment. It is possible that some patients will be determined to be ineligible between the time of consent and randomization assignment; these patients will not count toward the sample size goal. Research assistants will also be trained to assess potential symptoms of acute inflammation (swelling, warmth, pain flare); these Veterans will be evaluated by [name] or another health care provider prior to participation.

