6.0 Arthritis Education Intervention

Participants in the AE control group will receive low literacy educational materials via mail every two weeks. Because STEP-KOA is a multi-component intervention, with participants receiving different numbers of Steps, it is not possible to implement a control condition that will mirror the exact intervention "dose" received by all participants in the STEP-KOA group. However, AE will achieve the goal of providing an active, OA-related control condition. We selected a mail format because it mirrors the "remote" aspect of the Step 1 intervention that will be received by all study participants in the STEP-KOA group. We selected the two week interval for mailings because it mirrors aspects of each of the STEP-KOA interventions: Step 1 includes feedback regarding potential changes in exercise level on a two-week basis, Step 2 involves biweekly phone calls, and Step 3 involves PT visits spaced approximately 2 weeks apart. The AE intervention will include a comprehensive set of topics related to OA and its management, based on established treatment guidelines (Box 1)^{17,73}. These materials will be based on those we have already developed and successfully utilized in prior HSR&D funded clinical trials among Veterans with OA^{16,26}.

Box 1. Topics for AE Intervention

- What is OA?
- Diagnosis of OA
- Risk Factors for OA
- Health Care Providers And OA
- Pain Medications (Oral)
- Topical Pain Medications
- Joint Injections
- Knee Braces
- Shoes and Orthotics
- Physical Activity
- Weight Management
- Joint Protection
- Pain Coping Skills
- Surgery
- Complementary and Alternative Therapies
- OA and Sleep
- OA and Mental Health
- OA and Fatigue

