7.0 Measures

Study assessments will be conducted in person at baseline and 9-months (primary outcome point); interim assessments (3-months, 6-months) and longer-term follow-up (15-months) will be conducted via telephone. Assessments will be conducted by a research assistant blinded to group assignment. Participants will be paid \$40 for in-person and \$20 for telephone-based assessments. This measurement battery is shorter in length than those from our recent clinical trials among veterans with knee OA^{26,44}, and the time burden has been

acceptable to participants, with little missing data. Prior to each assessment point (either on the phone at the time of scheduling, on the phone just before assessments begin, or in-person at the time of assessment), a study team member will ask participants whether they have had any new health problems since their last assessment point. If there are new health problems, the study team will ask the nature of these problems. If these problems are related to exclusion criteria, the study team member will either: 1) Let the participant know they need to be withdrawn from the study OR 2) If it is unclear whether withdrawal is appropriate, let the participant know they will contact a clinical co-investigator and follow-up to let them know if they are eligible to continue in the study; assessments will not proceed until this is resolved. At in-person follow-up visits, research assistants will measure the participants Resting Blood Pressure; if diastolic blood pressure >110mm/Hg or systolic >200mm/Hg will be advised to be seen at the Emergency Department or Urgent Care immediately. Assessments will not proceed until these issues are resolved.

7.1 Primary Outcome: WOMAC. The primary outcome measure is the WOMAC, a measure of lower extremity pain (5 items), stiffness (2 items), and function (17 items), with items rated on a Likert scale of 0 (no symptoms) to 4 (extreme symptoms). The reliability and validity of the WOMAC total score and subscales have been confirmed⁷⁴. The WOMAC has been widely used in trials behavioral interventions for knee OA, confirming its sensitivity to change. The WOMAC has also been validated for use via telephone⁷⁵. To supplement the WOMAC, we will add additional measures that are part of the widely used Knee Osteoarthritis Outcome Survey (KOOS).

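### Section 7.0 withdraws participants from the study for exclusion-related health problems without separating this from outcome collection, so some WOMAC scores are lost that could still be obtained

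*Combined protocol and SAP*

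**What the plan says.** Section 7.0 (Measures) places a health check before every assessment, in both arms. If a participant reports a new problem, "the study team will ask the nature of these problems". If it relates to an exclusion criterion, there are two routes. In the first, "the study team member will either: 1) Let the participant know they need to be withdrawn from the study". In the second, for unclear cases, staff tell the participant that "they will contact a clinical co-investigator and follow-up to let them know if they are eligible to continue in the study", and no assessment takes place until that is settled.

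The exclusion criteria in Section C.3.0 are mixed. Some bear on the ability to self-report, such as "Dementia; Psychosis; Active substance abuse disorder" or severe hearing impairment. Others are physical or time-limited events: meniscus or ACL tear, major lower-extremity surgery, cardiovascular hospitalisation. One is a judgement: "Other health problem that would prohibit participation in the study and/or warrant immediate PT".

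Other sections bear on the point:

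- Section 7.1: "The WOMAC has also been validated for use via telephone". Under 7.0 the 3-, 6- and 15-month assessments are by telephone anyway.
- Section 5.4: participants who receive no Step 3 physical therapy may stay in the study.
- Section 7.10: new OA treatments do not lead to exclusion. Joint-replacement patients are left out of WOMAC analyses, but the proportions having that surgery are compared between arms.
- Section 8.1: the primary analysis is intention-to-treat.
- Section 8.4: likelihood estimation under missing at random, with multiple imputation if missingness relates to other measured factors.

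**The concern.** Under the first route in 7.0, what ends is participation in the study, not only the exercise programme. No supplied section provides for a WOMAC afterwards. Because the check comes before the assessment, a problem reported at 9 months can remove the primary outcome at that visit, and scores go missing just when health has changed.

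Part of the loss is avoidable. Section C.4.0, on enrolment, speaks of "Study exclusion criteria (described above) that may make it unsafe to participate in regular activity". A danger from exercise is a reason to stop exercise or a physical test; it is not in itself a reason to stop a telephone questionnaire. A knee injury, non-replacement surgery or a cardiac admission does not by itself prevent self-report, and may well affect the score.

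The missing-at-random conditions in 8.4 (treatment, prior outcome, baseline covariates in the model) cover these losses only as far as earlier scores already reflect the event. The recorded nature of the problem could enter the multiple imputation, but post-event scores to impute from would exist only for participants cleared to continue. At stake are the 9-month between-arm comparison (Aim 1) and the 9-to-15-month change within STEP-KOA (Aim 2), where balance between arms gives no protection.

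**Working it through.** **The plan's own figure.** Inputs from 8.5: SD 17.5, baseline-to-follow-up correlation 0.4, effect size 0.33, two-sided 0.05, 80% power, 2:1 allocation, 20% attrition. The two-sample calculation gives 109 in AE. 109 × (1 − 0.4²) = 109 × 0.84 = 91.6, so 92 completers. 92 / 0.80 = 115 in AE, 230 in STEP-KOA, 345 in total. The sample size reproduces and is not in dispute.

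**Precision at 9 months.** With 184 and 92 completers, SE = 17.5 × √0.84 × √(1/184 + 1/92) = 2.05. Power for 5.8 points (noncentral t, 274 df) is 80.6%. The critical difference is 1.969 × 2.048 = 4.03.

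**Assumed inputs.** The documents give no rate for these withdrawals, so every rate, shift and sign below is an assumption. Let p1 and p0 be the shares withdrawn in the two arms, and c the amount by which their unrecorded WOMAC differs from what the model predicts for them.

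**Aim 1.** Bias = (p1 − p0) × c when c is the same in both arms.

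- Equal rates and equal shifts: zero.
- 6% vs 3%, c = 5: 0.03 × 5 = 0.15 points (0.15 / 2.05 = 0.07 SE).
- 10% vs 5%, c = 15: 0.05 × 15 = 0.75 points (0.37 SE).
- Swapping the arms or reversing c reverses the sign.
- If half the shift already shows at 6 months, bias = (p1 − p0) × (c − b × c/2), where b is the slope of the 9-month on the 6-month score: 0.222 if all correlations are 0.4, 0.391 if follow-up visits correlate at 0.7. The range becomes 0.12 to 0.67 points.

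These rates correspond to 14 to 29 people: 230 × 0.03 + 115 × 0.06 = 14 and 230 × 0.10 + 115 × 0.05 = 29.

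**Effect on the test.** At a bias of 0.15, the chance of significance at a true 5.8 becomes 78.5% or 82.5%. At 0.75 it becomes about 69% or 89%, and the type I error goes from 5.0% to 6.5%. An observed 5.8 stays significant until the bias reaches 5.8 − 4.03 = 1.77 points. At 10% vs 5% that needs a shift of 1.77 / 0.05 = 35 points on a scale of 24 × 4 = 96.

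**Aim 2.** For people lost after the 9-month score, the contribution to the bias in the change is p × c: 0.03 × 5 = 0.15 to 0.06 × 15 = 0.90 points in either direction (7 to 14 of 230). People withdrawn earlier lack both scores and contribute p × (c15 − c9), which is zero if their shift is the same at both times. For scale, the SE of the change in 184 people is 17.5 × √(2(1 − r)) / √184 = 1.41 at r = 0.4 and 0.82 at r = 0.8, with r assumed.

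**The case against.** The rule is less mechanical than the first route suggests. Unclear cases are reviewed and may continue, and the time-limited or judgement criteria could plausibly take that route. Section 7.10 does not exclude people with new OA treatments, and handles joint replacement at the analysis stage, which would be largely redundant if 7.0 always ended participation. This stands: a reader might infer that every exclusion-related event ends follow-up, and the documents do not support that. It also shows that 7.0 and 7.10 need reconciling, since joint replacement and other major lower-extremity surgery are themselves listed in C.3.0.

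It might seem pointless to apply the rule to AE, where "Participants in the AE control group will receive low literacy educational materials via mail every two weeks". That reading does not hold. AE participants do physical tests at 9 months (7.0, 7.2) and are then offered the exercise website and counselling calls (C.1.0), so a safety check has a purpose in both arms. It is still not a reason to stop questionnaires.

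Section 7.0 gives no reason for withdrawal, and the sorting of criteria by whether they prevent self-report is an inference made here. For dementia, psychosis, severe hearing impairment or terminal illness, the loss may not be avoidable.

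Finally, 8.4 anticipates dropout and 8.5 allows for 20% attrition. That protects planned power if these losses fall within the allowance. It does not protect against bias.

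**Conclusion.** The point holds as a minor design weakness. Section 7.0 does not separate stopping the intervention or a physical test from stopping outcome collection, and some of the resulting loss is avoidable.

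Several stronger conclusions are tempting but unsupported. Missing at random is not shown to be false. Intention-to-treat is not shown to be breached, since nothing in 7.0 removes withdrawn participants' earlier scores or moves them out of their assigned arm. No direction of bias can be named: the same rule applies to both arms, so equal rates are the natural starting point, and with equal shifts the Aim 1 bias is zero. Even the largest assumed case would not overturn an observed 5.8.

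For Aim 2 the 0.15 to 0.90 range applies only to losses after 9 months, and its upper end is comparable with the standard error. All these sizes rest on assumed rates and shifts. Absence of a provision is judged on the supplied text; the consent form may contain one.

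**What to change.** In 7.0, leave the clinical decision to stop the intervention or a physical test as it is, and state separately what happens to follow-up. Unless consent is withdrawn, or valid self-report is not possible or reasonable, keep collecting the WOMAC and other questionnaires at the time points already planned for that arm (3, 6, 9 and 15 months in STEP-KOA; 3, 6 and 9 in AE), by telephone if needed, and include them in the intention-to-treat analysis. If the consent form already provides for this, say so in 7.0.

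Record the reason and date of each such withdrawal by arm. For scores still missing, add a delta-adjusted sensitivity analysis within the multiple imputation of 8.4, with shifts in both directions over a range the sponsor justifies, by arm for Aim 1 and within STEP-KOA for Aim 2. Reconcile 7.0, 7.10 and 8.1 on follow-up and analysis after non-replacement lower-extremity surgery. The joint-replacement analysis rule in 7.10 is not changed by this.

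The cost is protocol and IRB wording, one data field, some programming, and a small number of already planned assessments. At the highest assumed rates, with everyone in the first two groups withdrawn at 3 months and a further 14 lost only at 15 months: 23 STEP-KOA × 4 + 6 AE × 3 + 14 STEP-KOA × 1 = 124 assessments. At $20 by telephone that is $2,480. With the 9-month visit at $40 it is 23 × $100 + 6 × $80 + 14 × $20 = $3,060. Staff time is extra, and the rates are assumed, so this is not a ceiling.

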7.6 Physical Activity, Adherence and Related Measures

Physical Activity Scale for the Elderly (PASE). The PASE is a self-report, 12-item scale that measures occupational, household, and leisure activity during a one-week period.⁷⁹ This scale was developed for use among older adults and is appropriate for patients with knee OA who typically have more limited physical activity than the general population. The PASE has been validated for use via telephone.

Additional Self-Report Physical Activity Items. We are also specifically interested in purposeful exercise behaviors. We will ask participants to report the number of times and minutes per week, on average, they are completing strengthening, stretching, and aerobic exercises

Adherence to Intervention Step Components. As described above, participants' use of the VET-KOA website will be logged within the site. For participants who advance to Step 2, we will collect information on the number of scheduled phone calls completed, and for participants who advance to Step 3, we will collect information on the number of scheduled PT visits attended.

7.7 OMERACT-OARSI Responder Criteria (for determining progression to intervention Steps)³⁶. We will use single item numeric rating scales to assess average pain and function during the prior two weeks (0=no pain / no difficulties with function to 100 = pain / difficulties with function as bad as you can imagine). Similar to prior research⁶², we will use the Patient Global Impression of Improvement scale for the third domain, with improvement defined as "better" or "much better." We have chosen not to use WOMAC scores in the construction of these criteria, since this is the primary study outcome. Prior clinical trials have also utilized both OMERACT-OARSI responder criteria and WOMAC scores as separate, distinct outcomes^{2,63,64}. Whereas the OMERACT-OARSI criteria simply designate individuals as responders vs. non-responders, WOMAC scores describe the degree of response or change in pain and function.

7.8 Participant Characteristics Associated with Treatment Response. Specific Aim 3 will evaluate participant characteristics associated with treatment response and the need for intensification to Steps 2 and / or 3 (See Section C.8.3). We will focus on four *a priori* characteristics we believe have strong potential for predicting the need of intervention intensification: age, baseline self-reported pain and function (single items described above for the Responder Criteria), and baseline self-rated general health (excellent, very good, or good vs. fair or poor). We have selected these measures because they are single items that could be quickly and easily administered in a clinical setting to guide referral to a specific treatment most likely to meet patients' needs.

7.9 Additional Participant Characteristics. We will assess the following to describe the study sample: age, race / ethnicity, gender, household financial state, education level, work status marital status, body mass index, questions about internet and technology use, the Patient Activation Measure, , comorbid illnesses (Self-Administered Comorbidity Questionnaire)⁸¹, joints with OA (including designation of unilateral vs. bilateral knee OA), duration of OA symptoms, and documentation of variables to verify an OA diagnosis based on American College of Rheumatology Clinical Criteria (duration of morning stiffness, presence of bony tenderness and bony enlargement, crepitus).

7.10 Knee OA and Related Care During Study Period. We will assess use of treatments for knee OA at baseline and follow-up assessments, including pain medications, topical creams, knee braces, joint injections, and assistive devices. We will assess this via self-report, as well as using VA medical records to identify receipt of physical therapy for knee OA, participation in MOVE!, and prescription pain medication use. We may also examine Fee Basis files to more comprehensively assess care received outside the VA. We will not exclude participants who have new OA treatments during the study period. However, it is important to evaluate whether there are differences in these treatments across study groups. If differences are observed, we will conduct two types of sensitivity analyses: a.) participants who received specific treatments will be excluded from analyses, b.) the specific treatment (e.g., new MOVE! participation) will be included as a covariate in statistical models. In addition, if we find that $\geq 20\%$ of participants have a change in any given type of treatment, we will conduct a sensitivity analysis that removes these participants. Because of the drastic improvements typically associated with joint replacement surgery, participants having this surgery during the study period will not be included in analyses of WOMAC scores. However, since receipt of total joint replacement is also an important OA outcome, we will compare the proportions of participants in each study group who receive this surgery during the study period.

